2.1 Objectives & Hypotheses

Objective - The primary objective is to develop “real world” strategies for the successful treatment of hepatitis C hemodialysis patients using Zepatier in a hemodialysis unit with a high prevalence of hepatitis C to improve patient outcomes and to reduce the risk of in-facility transmission of hepatitis C. These strategies developed will be primarily directed to Nephrologists and Hemodialysis Personnel (Nurses, Social Workers, Dieticians) in order that these individuals will gain the knowledge to administer a hepatitis C eradication program using Zepatier in their hemodialysis centers

Hypothesis – Hemodialysis patients have an increased prevalence of hepatitis C infection. Zepatier has been shown to be highly efficacious in the treatment of hepatitis C in hemodialysis patients. Current guidelines targeted to nephrologists for treatment of hepatitis C hemodialysis patients which incorporate DAAs have not been published. The hypothesis of this protocol is that guidelines for successful treatment of hemodialysis patients using current therapies such as Zepatier which can be implemented and managed primarily by nephrologists and hemodialysis personnel.

2.2 Background & Rationale, Significance of Selected Topic & Preliminary Data

- 1. Hemodialysis patients have an exceptionally high prevalence of hepatitis C, with prevalence rates up to 25% in urban hemodialysis units in the United States and greater than 50% in less developed countries.**
- 2. It has been estimated that by 2020, 775,000 patients with ESRD will need dialysis in the United States and 109,000 of these patients will be infected with hepatitis C.**
- 3. Hepatitis C is associated with an increased mortality among hemodialysis patients with a relative risk of 1.59 (95% CI, 1.33- 1.86).**
- 4. Kidney transplant recipients with hepatitis C also have an increased mortality with a relative risk of 1.79 (95% CI. 1.57-2.03). In addition hepatitis C infected transplant patients have an increased death rate from infection in the early (< 6 months) post-transplant period and a decreased graft survival.**
- 5. Attempts to prevent nosocomial transmission of hepatitis C in dialysis units by implementing universal precautions have not been consistently successful.**
- 6. The introduction of direct acting antivirals (DAAs) in 2011 as a treatment of hepatitis C patients has created a paradigm treatment shift for these patients. The DAAs have been shown to be highly effective with SVR rates greater than 90 to 95% in**

treatment naïve hepatitis C infected patients in the general population

7. One DAA, Zepatier is well suited for treatment of hemodialysis patients as well as patients with stage 4 or 5 chronic kidney disease not requiring hemodialysis since less than 1% of this DAA is excreted by the kidney. A recent randomized double-blind multicenter study compared Zepatier to placebo in stage 4 and 5 chronic kidney disease patients most of whom were hemodialysis dependent (77%) and who had infection with hepatitis C genotype 1. A SVR at 12 weeks after the end of therapy was achieved in 99% of patients who received Zepatier.

8. The majority of hemodialysis patient care is provided by nephrologists and hemodialysis healthcare personnel. Both of these caregiver groups have become quite adept at providing protocol driven medical care uniquely suited to this population and care setting. Although hemodialysis patients often have primary care providers and other medical specialists who participate in their care, dialysis patients are often reluctant to see these non-Nephrology physicians due to their demanding dialysis schedule. Furthermore, non-Nephrology providers often feel uncomfortable providing care and prescribing medications to patients with severely impaired renal function.

9. Thus, nephrologists and hemodialysis personnel are uniquely situated to implement and monitor treatment protocols using DAAs such as Zepatier in dialysis unit patients with hepatitis C infection. Clear and current guidelines for the implementation and monitoring of DAA treatment protocols in the hemodialysis population currently do not exist, and the development of such guidelines is one of the purposes of this protocol.

10. While nephrologists and hemodialysis health care personnel are aware of the prevalence of hepatitis C in hemodialysis patients and that DAAs are now available for treatment of such patients, most nephrologists and hemodialysis personnel are not aware of the specific “real world” steps required to identify and treat such patients

11. Another purpose of this protocol is to provide the specific “real world” steps which must be taken to successfully treat hepatitis C hemodialysis patients with DAAs. Application of these steps will allow hemodialysis units to implement guidelines which will allow DAA treatment of all eligible patients in a timely manner, thus reducing or eliminating the health consequences of hepatitis C infection in this special population.

12. This “real world” protocol will be developed and implemented by a diverse group of investigators, each with a unique area of expertise needed for such a protocol development with “real world” implementation. Members of the investigative

team include physicians with expertise in nephrology, hepatology, infectious disease, infection control, transplant nephrology and non-physician personnel with expertise in clinical pharmacology and hemodialysis social services.

13. The specific “real world” measures to be developed and summarized in this protocol are:

- a. Identify hepatitis C patients who meet the virologic and medical criteria for treatment with Zepatier alone or in combination with ribavirin
- b. Identify necessary pretreatment clinical and laboratory assessments that are needed before initiating treatment with Zepatier including those necessary for third party payment approval.
- c. Identify appropriate treatment candidates and obtain third-party payment approval.
- d. Identify clinical and laboratory testing to monitor during treatment.
- e. Perform post-treatment testing of sustained virologic response to treatment (SVR at 12 weeks).
- f. Identify barriers to third-party payment of treatment and steps necessary to overcome these barriers.
- g. Identify the roles of a clinical pharmacologist and non-physician health care personnel such as a dialysis nurse, social worker, and dietician in a Zepatier treatment protocol of hepatitis C infected dialysis patients.
- h. Identify available patient assistance programs for drug obtainment and criteria needed to qualify for such assistance.

2.3 Study Design

This is an interventional, prospective, non-randomized, non-blinded trial to evaluate real world strategies to identify and treat hepatitis C infected hemodialysis patients with Zepatier.

Based on a recent surveillance evaluation, there are approximately 30 patients in the hemodialysis unit with hepatitis C antibody of whom approximately 25 will qualify for therapy with Zepatier alone or in combination with Ribavirin.

Patients with known HCV infection defined by positive anti-HCV ab (prevalent positives) will be identified from review of the dialysis unit electronic medical records. All anti-HCV antibody positive patients will undergo HCV quantitative RNA testing. Those found to have detectable HCV RNA will undergo HCV genotyping.

Patients who are hepatitis C PCR positive will proceed into additional screening and will sign a consent form at this time.

Other Inclusion Criteria

- a. Age: Be greater than 18 on day of signing informed consent**
- b. HCV treatment status must fall into one of following categories (1) Naïve to all anti HCV treatment (2) Prior INF or PEG IFN + ribavirin treatment failures (null responders, partial responders, relapses) (3) Intolerant to prior INF or PEG-INF + ribavirin regimen (4) Prior HCV NS3/4A protease inhibitor failures.**
- c. Not of reproductive potential – hemodialysis patient with 12 months of no menses. Women of childbearing potential should use 2 reliable forms of contraception simultaneously during treatment and for 6 months after completion of therapy. This guideline will be applied for both Zepatier treatment alone or when combined with Ribavirin.**
- d. Males with partners of reproductive potential as long as contraception is used during and for 6 months after completion of therapy. This guideline will be applied for both Zepatier treatment alone or when combined with Ribavirin.**
- e. Understand the study procedures, alternative treatments available, risks involved with the study, and voluntarily agrees to participate by giving informed written consent.**

Exclusion Criteria

- a. Unable to provide informed consent**
- b. Currently undergoing active treatment with a direct acting antiviral agent**
- c. Have previously undergone successful treatment with a direct acting antiviral agent**
- d. Have moderate or severe hepatic impairment (Child-Pugh B or C)**
- e. Have evidence of decompensated liver disease manifested by presence or history of ascites, gastric or variceal bleeding, hepatic encephalopathy, or other signs/symptoms of advanced liver disease**
- f. Co-administration of known Hepatotoxic Drugs including but not limited to**
 - (1) Etofoxine**
 - (2) Isoniazid**
 - (3) Nitrofurantoin**
 - (4) Phenytoin**
- g. Patients receiving strong CYP3A/P-gp inhibitors, organic acid transporting polypeptide 1B1/3 inhibitors, strong inducers of cytochrome 450 3A (CYP3A), efavirenz, and other drugs which may interact as per Zepatier package insert.**
- h. Has a history of substance abuse with alcohol, intravenous**

drugs, psychotropics, narcotics, cocaine use within 1 year of screening or if shorter, is judged by the investigator to be capable of complying with study procedures.

i. Has a history of any condition, pre-study laboratory abnormality, or ECG abnormality or history of any illness which in the opinion of the investigator might confound the results of the study or pose additional risks from the administration of study drugs.

j. Has evidence or history of chronic hepatitis not caused by HCV including but not limited to nonalcoholic steatohepatitis (NASH), drug induced hepatitis, and autoimmune hepatitis.

k. Patients currently on a kidney transplant waiting list who have agreed to accept HCV positive organ offers.

l. All patients currently undergoing kidney transplant evaluation.

m. Laboratory Exclusion values#

(1). Hemoglobin less than 9 g/dL if patient will require concomitant ribavirin therapy

(2). Neutrophils less than 1,500/uL in Caucasians or less than 1,200/uL in Blacks

(3). Platelets less than 70,000/uL

(4). Direct bilirubin greater than 1.5 x ULN

(5). Total bilirubin greater than 1.6 unless history of Gilbert's disease

[figure not shown]
(6). Serum albumin less than 3.0 g/dL

(7). INR greater than 1.7 unless subject has stable INR on anticoagulation

(8). ALT or AST greater than 350

- if any of the laboratory exclusion criteria above are met, may have the abnormal value retested one time

2.4 Study Flowchart

2.5 Study Procedures

1. Patients who meet inclusion criteria and do not have exclusion criteria will have their clinical records reviewed by a hepatologist experienced in treatment of hepatitis C . Patients will only receive treatment with Zepatier if the hepatologist review determines them to be eligible for this study. The hepatologist during initial record review will also determine if the patient requires an in-person meeting with the hepatologist pre or post Zepatier treatment
- 2.. Patients who meet inclusion criteria and do not have exclusion criteria will be assigned treatment with Zepatier with or without Ribavirin according to following schedule:**
 - a. Drug Dosing**
 - (1). Zepatier : 100 mg grazoprevir and 50 mg elbasvir combination – one tablet per day
 - (2). Ribavirin – 200 mg per day
 - b. Drug Schedule**
 - (1). Genotype 1a – treatment naïve without baseline NS5A polymorphisms – Zepatier alone for 12 weeks
 - (2). Genotype 1a – treatment naïve with baseline NS5A polymorphisms – Zepatier and Ribavirin for 16 weeks
 - (3). Genotype 1b – treatment naïve – Zepatier 12 weeks

- (4). Genotype 1a or 1b – prior treatment with PegIFN/RBV and/or HCV NS3/4A protease inhibitor – Zepatier and Ribavirin for 12 weeks
- (5). Genotype 4 – treatment naïve – Zepatier for 12 weeks
- (6). Genotype 4 – prior treatment – Zepatier and Ribavirin for 16 weeks

3. . Subjects will be instructed to take Zepatier + ribavirin at bedtime. Phosphate binders should be taken at least 3 hours before or 3 hours after taking the Zepatier + ribavirin. If a subject misses a dose of Zepatier + ribavirin and it is less than 8 hours before the next dose, the missed dose should be skipped and the normal dosing schedule resumed. Subjects should not double the next dose to compensate for the missed dose.

4.. Subjects may withdraw consent at any time for any reason or be dropped from the trial at the discretion of the investigator should any untoward effect occur.

5.. Subject will be discontinued from treatment for any of following:

- a. Becomes pregnant during trial
- b. Investigator feels it is in best interest of subject to discontinue such as SAE which investigator feels if possibly or probably related to study medication.
- c. Abnormal LFT develop: if ALT increases to greater than 10x ULN and persistently remains greater than 10x ULN. Discontinuation as well if ALT elevation is accompanied by signs or symptoms of liver inflammation or increasing conjugated bilirubin, alkaline phosphatase, or INR.

6.. Role of Clinical Pharmacologist

- a. Confirming all patients meet inclusion and exclusion criteria
- b. Reviewing patient medications to identify medications which prevent participation or which require specific dosage adjustments or monitoring during the study
- c. Ensuring that all baseline studies have been performed and the results are entered into the clinical case record
- d. Schedule and review with PI all ongoing monitoring labs during active treatment
- e. Schedule and review with PI all post treatment monitoring labs
- f. Dispense Zepatier alone or with Ribavirin depending on presence or absence of polymorphism or prior treatment
- g. Monitor study participants for compliance with study medication
- h. Monitor study participants for any adverse events, record such adverse events in the clinical case record and determine

with the physician investigators if the study events are drug related

i. Obtain third-party approval for payment of study drugs

7.. Additional baseline/screening testing:

a. Hepatitis C genotype testing

b. Hepatitis C viral RNA load

c. Liver function tests

d. Protime (PT), INR, and Partial Thromboplastin Time (PTT)

e. HIV test – if positive determine if virus free on HAART, viral RNA load, and CD4 and T cell count

f. Liver biopsy (within 24 months of treatment) or Fibroscan (within 12 months of treatment)

g. History of alcohol use and alcohol testing when relevant

h. *Hepatitis BsAg and HepB cor Ab test - if the Hep BsAg or the Hep Bcore ab is positive, then obtain HBVdna at weeks 4, 8, 12 of therapy and at SVR12 post therapy*

i. For patients with Hepatitis genotype 1a, additional testing to determine if NS5A mutation is present or absent.

j. For patients with a history of intravenous or alcohol abuse, documentation will be needed to demonstrate that a discussion occurred with the patient discussing the risks of substance abuse and that the provider has offered to get substance abuse help for the patient

[figure not shown]
k. Additional baseline/screening testing/information will be obtained if requested by a third-party payer as a requirement for drug approval

l. Review of the clinical records for all candidate patients with a hepatologist or infectious disease physician with expertise in hepatitis C management before treatment is initiated to review all laboratory and clinical history data. At this review, there will be a determination of the fibrosis stage, including the presence or absence of cirrhosis and to guide optimal choice of therapy as well as determine if there is a need for long term cirrhosis management and liver cancer surveillance. In-person office visits with this physician will be determined on presence/absence of cirrhosis and otherwise on an as needed basis as determined by the dialysis nephrologist or hepatologist.

m. Treatment of HIV/HCV co-infected patients will need to be done in collaboration with the patient's primary HIV provider prior to starting and during HCV therapy to determine if any adjustments to the HIV regimen will need to be undertaken:

(1). Zepatier can be used with antiretroviral drugs which do not have significant interactions with Zepatier : abacavir, emtricitabine, enfuvirtide, lamivudine, raltegravir, dolutegravir, rilpivirine, and tenofovir. Other antiretroviral drugs allowed will be determined based on package insert, consultation with specialty

	
pharmacists, and the HIV treating physician Source - http://www.hcvguidelines.org/full-report/unique-patient-populations-patients-hivhcv-coninfection
 
(2). In patients who are taking warfarin, Protime and INR values will be obtained weekly during and following the study to determine if there are any alterations in the Protime and INR due to a Zepatier-Warfarin interaction. Any alterations will result in warfarin dosage adjustments to achieve therapeutic anticoagulation as measured by Protime and INR
 
8. . Testing/Evaluations During Active Treatment
 
a. Liver function tests and RNA viral load at week 4 (only in patients with Child’s A cirrhosis), 8, and 12 of treatment. For patients on 16 week therapy, LFT also at week 16.
 
b. In patients who are treated with combination of Zepatier and Ribavirin, hemoglobin monitoring every week during course of treatment
 
c. Clinical Pharmacology evaluation for compliance and adverse events at week 4, 8, and 12 (and week 16 for patients receiving a 16 week treatment course).
 
9.. Testing/Evaluation Post Treatment
 
a. RNA viral load at 12 weeks post treatment
 
b. Clinical Pharmacology evaluation 12 weeks post treatment for adverse events and determination if a SVR was achieved at 12 weeks post treatment
 
c. Patients who have a SVR at 12 weeks will be identified in the hemodialysis treatment records as hepatitis C ab positive but hepatitis C viral RNA PCR negative

2.6 Study Duration
	
It is estimated all subjects will be recruited and complete treatment over a 9 to 12 month period of time

2.7 Statistical Analysis and Sample Size Justification
	
The co-principle investigators [name] and [name] will be responsible for analyzing all data Since this study does not have a control or comparator group, issues of blinding are non-applicable
 
Statistical Methods
 
The planned primary analysis will be the proportion of patients who following treatment have achieved a SVR at 12 weeks following completion of treatment.

[figure not shown]

Secondary analyses will determine (a) proportion of patients for whom third party approval for Zepatier treatment was successfully obtained (b) logistic barriers to getting third party approval (c) adverse events with treatment

The design of this protocol does not require any specific statistical methods to test the hypothesis

Power/Sample Size:

A sample size to determine adequate statistical power is not applicable to this protocol since there is only one treatment group and the outcome is binary (SVR at 12 weeks achieved or not achieved) . However, the sample size of approximately 30 patients chosen for this study will be adequate to test the hypothesis and meet the objectives of this study

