
2.13 Protocol Submission for Investigator-Initiated Studies
	
U.S. protocols should be submitted by US investigators directly or through the Global Research Specialist at www.merckiisp.com
 
Non U.S. protocols should be submitted to the MSD office by the investigators.

Study Procedures

Hepatitis C antibody testing is performed routinely as per unit protocol for the clinical care of dialysis patients. These standard of care labs will be reviewed and Hepatitis C antibody positive patients identified. Patients will have a Hepatitis C viral load and genotype performed. Patients who are viral load positive and genotype 1 or 4 will be eligible to participate and approached about the study.

	Visit 0	Visit 1	Visit 2	Visit 3-5	Visit 6
Study week	prescreening	enrollment	1	4,8,12	24
Review HCV Ab results	X				
HCV viral load and genotype	X				
Sign informed consent		X			
NS5a testing		X (genotype1 only)			
LFTs, PT, PTT, INR, Hepatitis B, HIV		X			
Fibroscan or review of liver biopsy		X			
Referral to Hepatology		X (only for patients with cirrhosis)			
Referral to ID		X (only for patients with HIV)			
Review by Transplant Nephrology		X (evaluate potential for transplant, review listing status)			
Apply for Insurance approval		X			
Start study drug			X		
LFTs			X	X	
HCV VL			X	X	X
Hemoglobin			X (only if on Ribavirin)	X (only if on Ribavirin)	
Adverse event assessment				X	
Compliance assessment				X	

Patients who consent to participate will have a NS5A polymorphism checked in order to determine if Ribavirin administration is required. Study drug(s) will be administered as follows:

Genotype	NS5A	Prior treatment	Drug(s)	Duration
1a	no	no	Zepatier	12 weeks
	yes	no	Zepatier + Ribavirin	16 weeks
	no	yes	Zepatier + Ribavirin	12 weeks
1b	n/a	no	Zepatier	12 weeks
	n/a	yes	Zepatier + Ribavirin	12 weeks
4	n/a	no	Zepatier	12 weeks
	n/a	yes	Zepatier + Ribavirin	16 weeks

Subjects will be instructed to take Zepatier + ribavirin at bedtime. Phosphate binders should be taken at least 3 hours before or 3 hours after taking the Zepatier + ribavirin. If a subject misses a dose of Zepatier + ribavirin and it is less than 8 hours before the next dose, the missed dose should be skipped and the normal dosing schedule resumed. Subjects should not double the next dose to compensate for the missed dose.

Subjects may withdraw consent at any time for any reason or be dropped from the trial at the discretion of the investigator should any untoward effect occur.

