 - j. For patients with a history of intravenous or alcohol abuse, documentation will be needed to demonstrate that a discussion occurred with the patient discussing the risks of substance abuse and that the provider has offered to get substance abuse help for the patient
 - k. Additional baseline/screening testing/information will be obtained if requested by a third-party payer as a requirement for drug approval
 - l. One office visit for all candidate patients with a hepatologist or infectious disease physician with expertise in hepatitis C management before treatment is initiated to review all laboratory and clinical

history data. At this visit, there will be a determination of the fibrosis stage, including the presence or absence of cirrhosis and to guide optimal choice of therapy as well as determine if there is a need for long term cirrhosis management and liver cancer surveillance. Further office visits with this physician will be determined on presence/absence of cirrhosis and otherwise on an as needed basis as determined by the dialysis nephrologist.

m. Treatment of HIV/HCV co-infected patients will need to be done in collaboration with the patients primary HIV provider prior to starting and during HCV therapy to determine if any adjustments to the HIV regimen will need to be undertaken:

(1). Zepatier can be used with antiretroviral drugs which do not have significant interactions with Zepatier : abacavir, emtricitabine, enfuvirtide, lamivudine, raltegravir, dolutegravir, rilpivirine, and tenofovir. Other antiretroviral drugs allowed will be determined based on package insert, consultation with specialty pharmacists, and the HIV treating physician

Source - <http://www.hcvguidelines.org/full-report/unique-patient-populations-patients-hivhcv-coninfection>

Testing/Evaluations During Active Treatment

a. Liver function tests and RNA viral load at week 4 (only in patients with Childs A cirrhosis), 8, and 12 of treatment. For patients on 16 week therapy, LFT also at week 16.

b. In patients who are treated with combination of Zepatier and Ribavirin, hemoglobin monitoring every week during course of treatment

c. Clinical Pharmacology evaluation for compliance and adverse events at week 4, 8, and 12 (and week 16 for patients receiving a 16 week treatment course).

Testing/Evaluation Post Treatment

a. RNA viral load at 12 weeks post treatment

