- Estimated length of time to enroll all subjects and complete the study
- Length of a subject's participation time in study
- Project date of the proposed study

We estimate this study will take no more than 1 year to complete. We have already identified all of the Hepatitis C antibody positive patients in the dialysis unit via routine clinical screening for Hepatitis C performed for standard of care dialysis center protocol. We anticipate study participants will require 9 months to complete the study. We anticipate it will take up to 3 months to obtain all of the necessary laboratory results and insurance approvals to obtain Zepatier. Patients will be treated for 12-16 weeks depending on resistance testing results. We will then follow the patients for 12 weeks after the completion of therapy to prove they have achieved a sustained viral response (SVR) or cure.

Resources necessary for human research protection

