- Describe the follow-up of subjects and identify any procedures that are performed exclusively for research purposes or performed more frequently than would be clinically indicated (eg: additional x-rays)
- You may upload additional documentation using the **Upload** button below

Since this is a real-world study, all procedures and interactions performed are standard of care in the treatment of dialysis patients with Hepatitis C infection. We will review standard of care Hepatitis C antibody results and follow up any positive results with a Hepatitis C viral load and genotype. Patients who are viral load positive with genotype 1 or 4 infection will be approached about study participation during a standard of care dialysis visit. Patients who consent to the study will have LFTs, Hg, PT, PTT, INR, HIV and Hepatitis B testing performed, these are all the standard laboratory testing required to safely initiate Hepatitis C treatment. We will refer all patients to Hepatology for an evaluation of their fibrosis stage (either by biopsy or fibroscan, at the discretion of the hepatologist); patients who have stage 4 fibrosis (ie cirrhosis) will only be treated in consultation with hepatology. Patients who are HIV co-infected will be referred to infectious disease and their treatment will only be undertaken in consultation with ID. Pharmacy will go through the necessary steps to obtain insurance approval for the medications but all medications will be provided by the study sponsor. Patients will be started on the study drug and have standard of care laboratory tests performed to monitor liver function while on the medication (LFTs and Hepatitis C viral load; hemoglobin will be followed in patients on ribavirin). Once the study drug is completed, patients will have a final Hepatitis C viral load checked 12 weeks after the completion of therapy to document a cure.

The following documents are currently attached to this item:

Procedures (studyprocedures.docx) Date uploaded: 02/27/2018 10:27:30 AM

Deception

No

Are you conducting research outside of the United States? *

No

Analysis Plan

- **Note:** If the statistical methods used are described in the detailed protocol, this section may reference the detailed protocol.

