Zepatier is FDA approved to treat Hepatitis C in dialysis patients. Therefore the risks of participating in this study are the same as the subject would encounter being treated with Zepatier in a non-study setting. These risks include side effects of nausea, headache and fatigue. There is the possibility of Hepatitis B reactivation with any treatment for Hepatitis C in patients who are co-infected, therefore we will monitor Hepatitis B levels in patients who are co-infected and if detectable, institute treatment for Hepatitis B in consultation with hepatology. When treating Hepatitis C there is always the possibility of liver inflammation and increases in LFTs, we will monitor these every 4 weeks. Patients with advanced liver disease (ie cirrhosis) are at risk for hepatic decompensation when being treated for Hepatitis C - we will not treat patients with cirrhosis ourselves, but instead refer them to hepatology and let hepatology manage their treatment. Patients who are on warfarin may have a Zepatier-Warfarin drug interaction - in these patients Protime and INR will be monitored weekly during the study

Potential Study Benefits

This study will provide clear benefit to participants as they will be treated for their Hepatitis C infection at no cost to them. They will also add to the general medical knowledge by demonstrating the feasibility of general nephrologists treating Hepatitis C infection and identifying the difficulties in achieving this.

Alternatives to Participation (optional)

If the participant chooses not to participate in this study, their doctor will continue to follow the standard of care practices at the University of Pennsylvania Health-System. The participant can also discuss this with their doctor at any time

Data and Safety Monitoring

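### The visit table marks haemoglobin for ribavirin patients only at weeks 1, 4, 8 and 12 and has no week-16 column, while the text requires it every week of a 12- or 16-week course

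*Protocol*

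**What the plan says.** **Text.** Section 2.5, item 8b, requires "hemoglobin monitoring every week during course of treatment" for anyone on Zepatier plus ribavirin. Item b under the same heading in the Study Procedures text after section 2.13 says the same.

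**Visit table (Study Procedures, after section 2.13).** The haemoglobin row is written for ribavirin patients: its entry is "X (only if on Ribavirin". It is filled under Visit 2 (week 1, when study drug starts) and Visits 3-5 (weeks 4, 8, 12). The only later column is Visit 6, week 24.

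**Course length.** Section 2.5, item 2b, assigns "Zepatier and Ribavirin for 16 weeks" to two groups: untreated genotype 1a with NS5A polymorphisms, and previously treated genotype 4. The Study duration entry of the Protocol Form states: "Patients will be treated for 12-16 weeks depending on resistance testing results".

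**Other week-16 assessments.** Item 8a adds: "For patients on 16 week therapy, LFT also at week 16". The pharmacology evaluation for compliance and adverse events is set for weeks 4, 8 and 12 "and week 16 for patients receiving a 16 week treatment course". The table has a place for neither.

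**Elsewhere.** The Procedures entry of the Protocol Form says only that "hemoglobin will be followed in patients on ribavirin", with no frequency. Nothing in the documents says whether the text or the table governs.

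**The concern.** A visit table is what staff commonly use to book tests. This one has a row specifically for ribavirin patients, and that row shows a much sparser schedule than the text. The missing week-16 column falls only on ribavirin patients, because no 16-week regimen omits ribavirin.

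The protocol itself treats haemoglobin as a ribavirin safety matter: exclusion m(1) bars a haemoglobin below 9 g/dL only where ribavirin will be needed. The discontinuation rules give an ALT threshold but no haemoglobin threshold, so acting on a fall depends on having a recent value and on the investigator's judgement. If the table were followed, a fall could be found weeks late, or not by any planned test after week 12.

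There is a smaller reporting consequence. Section 2.9, item 4, counts an unfavourable laboratory result as an adverse event, and adverse events are secondary analysis (c) in the protocol and the SAP. Patients tested on different schedules would have unequal chances of a recorded haemoglobin event.

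**Working it through.** The plan states no total for these tests, so there is no figure to reproduce. The check is a comparison of schedules and a count.

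**Inputs**
- Frequency in the text: one test per treatment week (section 2.5, item 8b).
- Weeks marked in the table: 1, 4, 8, 12.
- Ribavirin course lengths: 12 or 16 weeks (section 2.5, item 2b, and the regimen table in Study Procedures).

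**Step 1: who is affected.** The regimen table has 7 rows. Four contain ribavirin: 1a with polymorphism (16 weeks), 1a previously treated (12), 1b previously treated (12) and genotype 4 previously treated (16). Two rows last 16 weeks, and both contain ribavirin (2 of 2).

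**Step 2: tests required and tests marked**

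| Course | Text | Table | Unmarked weeks | Share unmarked |
|---|---|---|---|---|
| 12 weeks | 12 | 4 | 2, 3, 5, 6, 7, 9, 10, 11 (8 weeks) | 8/12 = 67% |
| 16 weeks | 16 | 4 | the same 8 plus 13, 14, 15, 16 (12 weeks) | 12/16 = 75% |

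**Step 3: gaps in the table.** 4 - 1 = 3 weeks, 8 - 4 = 4 weeks, 12 - 8 = 4 weeks, against 1 week in the text. In a 16-week course nothing is marked after week 12, although ribavirin continues for 16 - 12 = 4 more weeks.

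**Step 4: sensitivity to the week-1 value.** Visit 2 is the drug-start visit. If its haemoglobin is drawn before the first dose, the table has 3 on-treatment values, not 4. The unmarked share becomes 9/12 = 75% or 13/16 = 81%. The counts move by one; the conclusion does not change.

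**Step 5: the last column.** The post-treatment viral load is due 12 weeks after treatment ends. That is week 12 + 12 = 24 for a 12-week course and week 16 + 12 = 28 for a 16-week course. Visit 6 is labelled week 24 only, which is 24 - 16 = 8 weeks after a 16-week course. The on-treatment and follow-up columns both fit the 12-week course alone.

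**Step 6: is it an extraction fault?** The haemoglobin row lines up with the LFT row, which is also filled under Visit 2 and Visits 3-5. The layout looks intact.

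**The case against.** The best defence is that the table is an incomplete summary of formal visits and does not contradict the text. The weekly rule is explicit and stated twice. The table weeks are a subset of the weekly draws, so testing weekly satisfies both. The table also leaves out weekly INR for patients on warfarin and the HBV DNA tests, so it plainly does not list everything. One role, the clinical pharmacologist, schedules the monitoring laboratory tests with the principal investigator. This is one dialysis unit with about 30 subjects, whose blood is drawn at dialysis.

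Most of that stands, and it limits the weight of the point. It does not remove it. The table nowhere calls itself a summary, and it is not simply a reduced version of the text: it marks LFTs and viral load at week 1, which the on-treatment list does not ask for. It does give ribavirin patients a haemoglobin row, and the frequency in that row is wrong.

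Two supporting arguments carry little weight. The Potential Study Risks entry gives a frequency for liver tests ("increases in LFTs, we will monitor these every 4 weeks") and none for haemoglobin, but it does not discuss ribavirin at all. The lack of a haemoglobin stopping threshold is a separate matter, and discontinuation on the investigator's judgement is already allowed.

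A reader might also infer that baseline blood counts are missing, because the enrollment column names no haemoglobin, neutrophils or platelets. The documents do not support that. The section 2.4 flowchart is not visible in the available text, the section 2.5 list is headed as additional testing, and the Protocol Form names haemoglobin (as Hg) among the tests after consent. The exclusion limits, the retest rule and the pharmacologist's eligibility check all presuppose that these values are obtained.

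**Conclusion.** The inconsistency is real and of minor-to-moderate importance. For ribavirin patients the table marks 4 weeks (3 if the week-1 value is pre-dose) where the text requires 12 or 16, and it covers none of weeks 13-16. This assumes that weekly means one test per treatment week. Harm arises only if staff schedule from the table and overlook the text.

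Three stronger conclusions might be drawn, and none is supported:
- *Patients will go untested.* The text requires weekly tests, so the documents show a scheduling risk and not a plan to omit them.
- *The anaemia results will be biased by a stated amount.* The documents give neither the number of ribavirin patients nor an anaemia rate, so no figure can be calculated.
- *The primary analysis is affected.* Haemoglobin timing does not enter SVR12, which the text sets at 12 weeks after completion. The Visit 6 label needs correcting so that the table agrees with that definition for 16-week patients.

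**What to change.** In the Study Procedures visit table:
1. Change the haemoglobin row to *weekly to the end of the assigned course (week 12 or week 16), ribavirin patients only*.
2. Add a week-16 column for the two 16-week regimens, with haemoglobin, LFTs and the pharmacology evaluation.
3. Relabel Visit 6 as 12 weeks after the end of treatment: week 24 for 12-week courses, week 28 for 16-week courses. Adding week 16 without this would leave the table wrong for the same patients.

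In the Procedures entry of the Protocol Form, state that haemoglobin is tested weekly in patients on ribavirin.

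The cost is one row, one column, one relabelled visit and one sentence. No on-treatment test is added, because the text already requires all of them. If dosing has already ended, report which haemoglobin schedule was actually followed alongside the adverse-event results.
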